6 STUDY MATERIALS

6.1 Investigational Product

6.1.1 Identity of the investigational product and accessories

The Pelex Upp is intended to allow a patient to perform biofeedback-augmented PFMT non-invasively and at home. It is comprised of a patient contact interface, a connected handheld device, and disposable sensor arrays. The sensor array is a flexible circuit array holding a pair of sensing electrodes and a reference electrode which are connected to a male connector at one end. The patient contact interface, upon which the user sits after disrobing, has the sensor array embedded along the upper surface. A housing compartment within the patient contact interface will hold signal processing equipment, which will be connected to the sensor array externally via a female connector in the front of the patient contact interface. The signal processing equipment will also be separately connected via a cord on the side of the patient contact interface to the handheld device. The handheld device will have two LED systems, a power switch and battery compartment for housing of the power source. The two LED systems will include a “cadence” LED, which flashes in a pre-set pattern for the user to follow with contractions of their own pelvic floor muscles. It will also include a “response” LED, which allows the user to visualize the contraction of their pelvic floor muscles. The sensor array is disposable, and several replacement sensor arrays will be included, and can be changed at the user’s discretion.

The Pelex Upp is completely non-invasive and made of hypoallergenic, non-latex materials.

6.1.2 Safety issues

The device under investigation is completely non-invasive, and qualifies as a non-significant risk device based on Title 21 CFR 812.2 (c). Safety issues would include skin abrasions and contact allergic reactions from contact of bare skin with the flexible circuit array, which has a mild adhesive applied to it

6.1.3 Handling, storage, accountability

The Sponsor will provide the Investigator with a supply of study devices for conduct of the study. All devices will be logged into the device accountability log. If a device is used in the investigation it will be documented in the device accountability log. Devices returned to the Sponsor will be noted as such in the device accountability log. A final accounting of devices will be being presented in the final clinical study report.

The Investigator shall permit an investigational device to be used only in subjects enrolled in the study. The Investigator shall not supply an investigational device to any person not authorized to receive it.

The Investigator or designee shall document receipt, use, and disposition of the device as it relates to:

- The quantity of the device, dates of receipt, catalogue and lot numbers;
- The names of all persons who received each device; and
- Why and how many units of the device have been returned to Sponsor or otherwise have left the possession of the Investigator.

The devices must be stored separately from other clinical supplies. Opened, unused devices must be returned to the Sponsor or destroyed on site as directed by the Sponsor.

The use of the study device outside of this protocol is prohibited. Each investigational site will identify a designee who will be held responsible for controlling the devices and ensuring that a device is dispensed only for the purposes of this study. This designee will be expected to retain all unused study supplies until the completion of the study and/or until a representative of the Sponsor has inventoried and made arrangements to return the supplies to the Sponsor. Upon completion or termination of this investigation or the Investigator's part of this investigation, or at the request of the Sponsor, the Investigator shall return any remaining supply of the device or otherwise dispose of the device as directed by the Sponsor.

6.1.4 Required training

Each study participant will be given instruction materials to guide use of the investigational device.

6.1.5 External studies

In the event that plans are made to conduct additional studies, new protocols describing the relevant handling, storage, accountability, and training procedures will be prepared specifically for those studies.

6.2 Other Study Materials

6.2.1 Materials to be provided by study site

- Study notebooks to maintain study documents, including signed ICFs, all applicable information, and additional forms to be collected and retained by the study institution during the course of the study.
- Example spreadsheets for tracking patient information.

6.2.2 Materials to be provided by external testing facilities

No materials from external testing facilities will be given.

7 STUDY PROCEDURES

7.1 Workflow

The study design is a prospective cohort that enrolls adult female patients identified as having stress urinary incontinence via an online enrollment form to evaluate the effectiveness of the Pelex Upp in treatment of stress urinary incontinence. The treatment group will enroll 5 subjects. Following the granting of Informed Consent, subjects will be enrolled in the study within the prospective cohort and will complete a four-week course of biofeedback augmented PFMT using the Pelex Upp. Patients will complete a pre- and post-study urinary incontinence quality of life evaluation tool to assess response to the investigational device.

Subsequent treatment and work up will be dictated by the reported persistence of symptoms. Follow-up with care providers will be as needed, as determined by the patient.

[figure not shown]

Figure 1: Study Workflow

Item
1. Study Brochure
2. Prospective Subject Screening Questionnaire
3. Subject Consent Form
4. Instructional Materials
5. Study Package with Study Materials
6. Pre-Study Questionnaire
7. Post-Use Questionnaire
8. Study Initiation Check-in Communication
9. Mid-Study Check-in Communication
10. Post-Study Questionnaire
11. Thank You Communication

Table 1: Study Materials

7.2 Study Data

Eligible subjects will be invited to participate in the study on a first-come, first-serve basis. Potential donors must provide informed consent to participate. To be eligible for participation, subjects must be at least 18 years of age.

At the discretion of the Investigator and subject to Pelex requirements, urinary incontinence data will be collected from each eligible subject providing signed informed consent.

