Methodology Overview	
This will be a prospective cohort study of women > 18 years of age with symptoms of stress urinary incontinence, recruited via an online recruitment tool.
 
After screening, patients meeting inclusion criteria will be given a study brochure, and then given instructions on how to indicate desire to participate in the study. The patient will then be contacted for study participation, including explanation of study and details and completion of Informed Consent. Participants will then complete a pre-treatment urinary incontinence symptom questionnaire(ICIQ).
 
After completion of the above, the participants will then be given a Pelex Upp study, in addition to educational materials on use of the device, and a treatment schedule. Participants will perform a standardized biofeedback-mediated pelvic floor muscle training program with the study device 10 minutes a day, five times a week for 4 weeks. There will be a mid-study check in to assure all devices are functioning appropriately. At the end of the study, participants will complete a post-treatment urinary incontinence symptom questionnaire(ICIQ).
 
Endpoint of the study will be change in stress urinary incontinence symptoms as measured by the ICIQ. The ICIQ will be collected at 2 time points: before study entry, and at study close.

ABBREVIATIONS

PFMT	Pelvic floor muscle training
SUI	Stress urinary incontinence
OAB	Overactive bladder
UI	Urinary incontinence
PFM	Pelvic floor muscles
US/USA	United States of America

TABLE OF CONTENTS

1	INTRODUCTION	11
2	DESCRIPTION OF THE INVESTIGATIONAL PRODUCT	11
2.1	Overview	11
2.2	Proposed Intended Use Statement	11
3	STUDY OBJECTIVES	11
4	STUDY OVERVIEW	12
4.1	Study Approach	12
4.3	Study Duration.....	13
5	STUDY POPULATION	14
5.1	Sample Size and Target Study Population	14
5.1.1	Sample size	14
5.1.2	Study population	14
5.1.3	Alignment with intended study population.....	14
5.1.4	Alignment with intended use of the device.....	14
5.2	Recruitment Methods	14
5.2.1	Recruitment for Study	14
5.2.2	Duration of study activities.....	14
5.3	Patient Selection	15
6	STUDY MATERIALS	15
6.1	Investigational Product.....	15
6.1.1	Identity of the investigational product and accessories	15
6.1.2	Safety issues.....	16
6.1.3	Handling, storage, accountability.....	16
6.1.4	Required training.....	16
6.1.5	External studies.....	17
6.2	Other Study Materials	17
6.2.1	Materials to be provided by study site.....	17

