7.2.1 Collection of data

Source data is all information, original records of clinical findings, observations or other activities in a clinical trial necessary for the reconstruction and evaluation of the trial. Source data are contained in source documents. Examples of source documents in this study include medical records, memoranda, evaluation checklists, CRF worksheets, and Data Capture

An Electronic Data Capture (EDC) system using an electronic Case Report Form (eCRF) that is compliant with 21 CFR part 11 is the primary data collection instrument for the study. All data requested on the eCRF should be recorded. The EDC system will only allow for data to be collected based on specified fields. The EDC system also generates an audit trail for any corrected data. All data entered on an eCRF must be traceable to a source document.

eCRFs will be completed for each subject enrolled into the clinical study. The Investigator will review, approve, and electronically sign the completed eCRF for each subject; the Investigator's electronic signature will serve as a testament of the Investigator's responsibility for ensuring that all clinical data entered on the eCRFs are complete, accurate, and authentic.

Subjects will be identified in the EDC by a numeric code used for study purposes. Subjects are not identified by name. Data entry staff are expected to follow data protection practices. All procedures for the handling and analysis of data will be conducted using good computing practices meeting FDA guidelines for the handling and analysis of data for clinical trials.

Information about study subjects will be kept confidential and managed according to the requirements of the Health Insurance Portability and Accountability Act of 1996 (HIPAA). Those regulations require a signed subject authorization informing the subject of the following:

1. What protected health information (PHI) will be collected from subjects in this study;
2. Who will have access to that information and why;
3. Who will use or disclose that information; and
4. The rights of a research subject to revoke their authorization for use of their PHI.

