7.3 Randomization and Blinding

No randomization nor blinding will occur.

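### Section 7.2 makes collection of the incontinence outcome discretionary, which contradicts the unconditional collection set out elsewhere in the protocol

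*Protocol*

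**What the plan says.** The endpoint is defined in the Synopsis (Methodology Overview): "Endpoint of the study will be change in stress urinary incontinence symptoms as measured by the ICIQ". The same paragraph fixes the schedule: "The ICIQ will be collected at 2 time points: before study entry, and at study close". Section 7.1 agrees, though it does not name the instrument: "Patients will complete a pre- and post-study urinary incontinence quality of life evaluation tool to assess response to the investigational device". Neither place attaches a condition.

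Section 7.2.1 requires an electronic case report form for each enrolled subject and adds: "All data requested on the eCRF should be recorded".

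Section 7.2 is worded differently: "At the discretion of the Investigator and subject to Pelex requirements, urinary incontinence data will be collected from each eligible subject". It gives no ground on which the discretion may be used and does not say what the sponsor's requirements are.

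Three other provisions bear on the point:
- Section 11.3 lets the clinician decline to collect data, but only where collection carries an unusually high risk of harm or discomfort.
- Section 5.3 (Table 1) lists worsening of stress incontinence symptoms as a withdrawal criterion.
- Section 7.3 states: "No randomization nor blinding will occur".

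**The concern.** Urinary incontinence data are the endpoint of this study. One section makes their collection conditional on the judgement of an unblinded investigator and on the sponsor, while others make it unconditional. Both rules cannot govern. This is a conflict between stated rules, so it is not a detail that could be left to an analysis plan.

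The risk is outcome-dependent missing data. A woman who is doing badly may be withdrawn for worsening, and no section says that a withdrawn woman still completes the post-treatment questionnaire. Section 7.2 would permit that form not to be collected. Section 9.2 (Bias Minimization) covers only the order of enrolment. Section 9.3 aggregates the responses, which in practice means those that were obtained. With five women and no described control group, one or two missing forms can change the picture.

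**Working it through.** **Comparison of the rules on collection**

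| Place in protocol | Who supplies the outcome | Condition |
|---|---|---|
| Synopsis, Methodology Overview | Participants, before entry and at study close | None |
| Section 7.1 | Patients, pre- and post-study | None |
| Section 7.2.1 | Each enrolled subject has an eCRF; requested data to be recorded | None |
| Section 7.2 | Each eligible consenting subject | Investigator discretion and sponsor requirements, no criterion |
| Section 11.3 | Data may be left uncollected | Only for unusually high risk of harm or discomfort |

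Section 7.2 is the only place with an open condition. Section 11.3 already covers safety, so the open condition is not needed for that purpose.

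**Illustration of the possible bias**

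No figure in the protocol is in dispute. The sample size of 5 (Section 7.1) cannot be reproduced, because Section 9.1 gives no calculation and says none is needed. The protocol gives no SD for the ICIQ change, so the results below are in SD units.

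Assumptions: five independent, normally distributed changes with true mean zero, scored so that a higher value means more improvement, and the missing forms are exactly those of the women with the worst changes.

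Expected values of the five ordered changes, by numerical integration, in SD units: −1.163, −0.495, 0, +0.495, +1.163. They sum to zero, so the expected mean of all five is 0.

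- Worst 1 missing: the other four sum to 1.163, and 1.163 / 4 = **+0.29 SD**.
- Worst 2 missing: the other three sum to 0 + 0.495 + 1.163 = 1.658, and 1.658 / 3 = **+0.55 SD**.

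A simulation of 400,000 samples of five gave 0.291 and 0.553, in agreement.

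The same effect on a proportion, supposing that 3 of 5 women improve:

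- All five collected: 3/5 = 60%.
- One non-improver missing: 3/4 = 75%.
- Both non-improvers missing: 3/3 = 100%.

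**The case against.** A reader might infer that the protocol as a whole leaves outcome collection to the investigator. It does not. The Section 7.2 sentence itself refers to each eligible subject, and the Synopsis, Section 7.1 and Section 7.2.1 point to complete collection. The paragraph before the clause concerns invitation, consent and minimum age, and speaks of donors, which looks like text carried over from a template. The clause can therefore be read as a rule on who enters data collection, or as a loose reference to the Section 11.3 exception. These readings are plausible. They do not remove the conflict, because the clause sets no such limit and names neither entry nor safety.

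A reader might also infer that outcomes will be gathered selectively, or that selection would go unnoticed. The documents support neither. Nothing shows such an intent. Subjects enter their own responses (Section 8), and the stated purpose of the mid-study check-in is to confirm that devices work. With an eCRF for each subject and a device log naming everyone who received a device (Section 6.1.3), four questionnaires from five women would be seen. What might not be seen is the reason for the gap.

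The route to selection is not wholly hypothetical, however. Applying the worsening criterion in Section 5.3 during the four weeks means that the study team learns of worsening before the final questionnaire. Deleting the clause in Section 7.2 would not close that route by itself, so the fix must also cover women who are withdrawn.

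Finally, Section 9.1 calls the study exploratory, and the protocol names no inferential test. That lowers the stakes. Against it, Section 3 sets out to demonstrate efficacy and Section 5.1.1 makes efficacy the primary goal, so a biased summary of change would still bear on the main conclusion.

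**Conclusion.** The point holds as an internal contradiction. Section 7.2 states an open discretion over the endpoint data that conflicts with the Synopsis and Sections 7.1 and 7.2.1, and that goes beyond the bounded exception in Section 11.3. Taken literally, it permits outcome-dependent omission in an unblinded study of five women with no described control group.

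The shifts of 0.29 and 0.55 SD are upper-end illustrations. They rest on normal changes, a true mean of zero and the loss of exactly the worst one or two outcomes, and they do not predict what will happen. The documents do not establish that selective collection is planned or likely. The wording should be corrected because it bears on the endpoint and the correction costs almost nothing.

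**What to change.** 1. In Section 7.2, delete the opening clause on investigator discretion and sponsor requirements, or limit it expressly to the Section 11.3 exception.
2. State that the pre- and post-treatment ICIQ is requested from every enrolled subject, including those who stop training or are withdrawn. Allow two exceptions only: the Section 11.3 safety exception, and revocation of consent or authorization. Section 7.2.1 already provides for revoked authorization, and the new text should be consistent with it.
3. Report the numbers enrolled and analysed, with the reason for any missing questionnaire.

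The cost is a few sentences of protocol text. No new instrument is needed, because the questionnaire is already planned for everyone. The only added effort is to request it from women who stop early and to record why any form is missing.

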7.2.1 Collection of data

Source data is all information, original records of clinical findings, observations or other activities in a clinical trial necessary for the reconstruction and evaluation of the trial. Source data are contained in source documents. Examples of source documents in this study include medical records, memoranda, evaluation checklists, CRF worksheets, and Data Capture

An Electronic Data Capture (EDC) system using an electronic Case Report Form (eCRF) that is compliant with 21 CFR part 11 is the primary data collection instrument for the study. All data requested on the eCRF should be recorded. The EDC system will only allow for data to be collected based on specified fields. The EDC system also generates an audit trail for any corrected data. All data entered on an eCRF must be traceable to a source document.

eCRFs will be completed for each subject enrolled into the clinical study. The Investigator will review, approve, and electronically sign the completed eCRF for each subject; the Investigator's electronic signature will serve as a testament of the Investigator's responsibility for ensuring that all clinical data entered on the eCRFs are complete, accurate, and authentic.

Subjects will be identified in the EDC by a numeric code used for study purposes. Subjects are not identified by name. Data entry staff are expected to follow data protection practices. All procedures for the handling and analysis of data will be conducted using good computing practices meeting FDA guidelines for the handling and analysis of data for clinical trials.

Information about study subjects will be kept confidential and managed according to the requirements of the Health Insurance Portability and Accountability Act of 1996 (HIPAA). Those regulations require a signed subject authorization informing the subject of the following:

1. What protected health information (PHI) will be collected from subjects in this study;
2. Who will have access to that information and why;
3. Who will use or disclose that information; and
4. The rights of a research subject to revoke their authorization for use of their PHI.

In the event that a subject revokes authorization to collect or use PHI, the Investigator, by regulation, retains the ability to use all information collected prior to the revocation of subject authorization. For subjects that have revoked authorization to collect or use PHI, attempts should be made to obtain permission to collect at least vital status (i.e., that the subject is alive) at the end of their scheduled study period.

The accountability procedure will consist of Pelex, Inc., the principal investigator and project team lead, respectively, being responsible for upkeep of the secured database and the only people with access, except for the IRB. The IRB will be allowed to access site, records, etc.

7.3 Randomization and Blinding

No randomization nor blinding will occur.

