8 DATA QUALITY ASSURANCE

The study screening questionnaire, pre-study survey, post-use survey, and post-study survey are all forms requiring input from subjects. Pelex will endeavor to use electronic forms of data capture whenever possible. Possible forms of electronic data capture include Google

forms and SurveyMonkey. These forms will be configured such that only [name] has access to the raw information in order to protect patient health information.

While obtaining the informed consent, [name] will ask the subject whether she is able to use electronic data forms. In the event that the subject indicates that she is unable to use electronic data forms, then the study team will include a paper journal in the study package. The study package will be returned to [name] who will be responsible for converting the paper form to an electronic format, anonymizing the electronic version, and archiving or destroying the paper form.

Beyond subject input, the study device are intended to collect physiological parameters and store this data on the device. The data will be salvaged when the study materials are returned to the study team. The device data will only be stored using the anonymous subject identifier. Data stored on the device hardware that is returned to the study team will be recovered by [name] following a protocol that has been established with the primary device manufacturer, Arduino. Anonymized recovered data will be collectively stored in a password protected data server or database. The raw data will be backed up at least once to local storage.

The data will be processed through reproducible measures, such as by writing start-to-finish code. When data processing is complete, this code will be applied to a copy of backed-up raw data to confirm the reproducibility of the analysis and integrity of the raw data.

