9.2 Bias Minimization

All subjects meeting the specified eligibility criteria will be enrolled on a first-come, first-serve basis.

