9.3 Planned Analyses

Specific study parameters to be analyzed will be the maximum pelvic floor contraction at study entry and exit, as well as maximum sustained contraction at study entry and exit. Objective clinical response to use of device in improving SUI symptoms will also be captured per the symptom questionnaires, which will be entered into an electronic record, and then all responses will be aggregated.

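### Section 7.3 excludes all blinding, so the entry and exit contraction maxima of Section 9.3 may be derived by people who know the time point of each recording

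*Protocol*

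**What the plan says.** Protocol Section 7.3 is one sentence: "No randomization nor blinding will occur". It names no role and makes no exception.

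Section 9.3 gives as the parameters to be analysed "maximum pelvic floor contraction at study entry and exit, as well as maximum sustained contraction at study entry and exit". Symptom questionnaires are captured as well.

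Section 8 covers the device data. They reach the study team late: "The data will be salvaged when the study materials are returned to the study team". On masking it says "The device data will only be stored using the anonymous subject identifier". On processing it says "The data will be processed through reproducible measures, such as by writing start-to-finish code", and the check on that code is: "When data processing is complete, this code will be applied to a copy of backed-up raw data to confirm the reproducibility of the analysis".

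Section 9.2, the section on bias, contains one measure: "All subjects meeting the specified eligibility criteria will be enrolled on a first-come, first-serve basis".

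The synopsis names the change in ICIQ as the endpoint. Section 9.1 calls the study exploratory, and Section 7.1 plans 5 women in one treatment group.

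**The concern.** Women who operate the device cannot be blinded to it. The people who turn a recording into a maximum can be blinded to its time point, and Section 7.3 as worded rules that out along with everything else.

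A maximum is sensitive to how the signal is handled: how it is smoothed, what is discarded as artefact, what counts as a contraction and how long it must last to be sustained. If any of these choices is made off-line with entry and exit labels visible, an expectation of improvement can enter the result unnoticed. The sponsor's own team handles the data (Sections 7.2.1 and 8), and Section 1 says the results will be used to verify that the technology works as expected. With five women and no comparator arm, little else in the design would expose such an effect.

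**Working it through.** The plan gives no figure on this point, so there is none to reproduce. The check is a comparison of the sections, followed by an illustration of size.

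**Comparison of the sections**

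1. *Do the Section 9.3 maxima come from the recordings?* Section 9.3 does not say so outright. Section 8 says the device records and stores physiological parameters, and no other way of measuring contraction is described. I take the recordings as the source.
2. *Is the time point hidden anywhere?* The storage rule in Section 8 removes identity only. Section 9.3 needs entry and exit told apart at some stage, and nothing says that this is withheld until the maxima have been derived. Section 7.3 says no blinding occurs.
3. *Does the re-run in Section 8 protect against this?* No. The same code applied to a copy of the same raw data returns the same answer, whatever was known when its settings were chosen.
4. *Does Section 9.2 protect against this?* No. Enrolment order has no bearing on how a signal is processed.
5. *Could an SAP supply the protection?* An SAP could fix the algorithm in advance. It could not mask the time point without contradicting Section 7.3 as it stands.

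**Illustration of size**

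Only n = 5 comes from the protocol (Section 7.1). The rest is assumed: a true change of zero, a within-woman change with SD 1 under each setting, m candidate settings whose results have common correlation ρ, and the setting with the largest mean gain always reported.

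The expected false mean gain is e(m) × √(1 − ρ) / √n, where e(m) is the expected maximum of m independent standard normal values: e(3) = 0.846, e(6) = 1.267, e(10) = 1.539.

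- Smallest case, m = 3, ρ = 0.9: 0.846 × √0.1 / √5 = 0.12 SD
- Middle case, m = 6, ρ = 0.7: 1.267 × √0.3 / √5 = 0.31 SD
- Largest case, m = 10, ρ = 0.5: 1.539 × √0.5 / √5 = 0.49 SD

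| Settings m | ρ = 0.5 | ρ = 0.7 | ρ = 0.9 |
|---|---|---|---|
| 3 | 0.27 | 0.21 | 0.12 |
| 6 | 0.40 | 0.31 | 0.18 |
| 10 | 0.49 | 0.38 | 0.22 |

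Simulation of the same model gives the same values. In the middle case the reported mean is positive 78% of the time, against 50% with one fixed setting.

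For scale, the standard error of an unbiased mean change in five women is 1/√5 = 0.45 SD. Only the largest of the nine cases exceeds it.

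**The case against.** **The protocol does not say that the code is developed on these recordings.** This stands. A reader might infer it from the order in Section 8, where processing is completed and the code is then re-run. That order dates the check and does not say when the algorithm is fixed. Definitions of the maxima and a code lock are ordinary SAP content, and their absence from the protocol is no finding.

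**Section 7.3 is a routine statement about treatment in a single-group study.** That may be the intent. The wording still covers every role, so it would bar masked processing even if an SAP proposed it. Narrowing the sentence keeps the likely intent.

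**The named endpoint is untouched.** This stands. The ICIQ is self-reported and involves no signal processing, and neither objective in Section 3 names contraction strength. The point concerns only the Section 9.3 maxima.

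**There may be little left to choose off-line.** Sections 2.1 and 6.1.1 describe signal processing within the device. Section 8 also speaks of raw data and of processing code, so some choice probably remains. How much is not stated.

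**The illustration is a worst case in a study without a planned test.** This stands as a limit on weight. The number of settings and the correlations are assumed, and always reporting the most favourable setting is extreme. The bias would nevertheless lie in the reported change itself, with or without a p-value.

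**Scripted processing and retained raw data are safeguards.** They are, in part: others can repeat the analysis with different settings later. They do not hide the time point when the result is first derived.

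**Conclusion.** The point holds in a limited form. Section 7.3 excludes all blinding, Section 8 does not hide the time point, and the re-run does not make up for that. The plan therefore permits the two contraction maxima to be derived with knowledge of which recordings are entry and which are exit.

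A reader might go further and conclude that the code will be tuned to show a gain, or that the efficacy result is compromised. The documents support neither: they describe no tuning, and the ICIQ endpoint does not depend on the recordings.

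The size of any bias cannot be derived from the documents. The range of about 0.1 to 0.5 SD is conditional on 3 to 10 settings, correlations of 0.5 to 0.9 and the most favourable setting always being reported. In an exploratory study of five women this is worth correcting because the correction is cheap, and it is no reason to hold the study.

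**What to change.** - **Section 7.3:** replace the sentence with: *No randomization; participants and investigators are not blinded.*
- **Section 8:** add that, at data recovery, a script relabels the entry and exit recordings with random codes that hide date and session order, and that the key is merged only after both contraction measures have been derived. Adjust the sentence on the subject identifier so that the stored files may carry these codes.
- **Section 9.2:** list this masking as a bias control.

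The cost is one short script and a rule on when the key is opened. The synopsis schedule implies up to 5 × 4 = 20 sessions per woman, so the script must select the entry and exit sessions by date before it codes them. With so few people having access to the database, the key can be written to a file that stays unopened until the measures exist. That depends on discipline more than on separation of staff, but needs no new post, procedure or participant. The small downside is that recordings cannot be inspected by time point until the measures have been derived.
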